### **13. Collaborators**

This study is designed and will be conducted in collaboration with academic researchers, Reckitt Benckiser and Spink Health. Reckitt Benckiser (RB) is a British multinational consumer goods company that makes products like Dettol. Spink Health is a healthcare agency that creates and executes inspirational campaigns. All collaborators contributed to the protocol. Spink Health is charged with writing the corporate report back to RB, with the academic team acting as consultants. The academic team are charged with writing an academic report for publication in an academic press.

### **14. Acknowledgment statement**

The funder and collaborators support will be acknowledged in reports/presentations with the following message: *This research was funded by the Global Hygiene Council and designed in collaboration with Reckitt Benckiser Group plc and Spink Health. The analyses were conducted solely by academic team, and the views expressed in the article are those of the authors and do not necessarily represent the views of the funder.*

### **15. Ethical Considerations**

This study will be approved by the University's ethical review board before data collection begins.

Note that the study should be considered low risk to participants, as the survey data will be completely anonymously, the content is not sensitive and participants' can easily withdraw by closing their browser window.

Appendix A. Survey items (finalized 09-Apr-2020)

Domain	Question Number	Handwashing Surface Disinfection	Parents	Teachers
Knowledge An awareness of the existence of something	1	H	I know that my children should wash their hands with soap and water for at least 20 seconds.	I know that my pupils should wash their hands with soap and water for at least 20 seconds.
	2	H	(RS) I do not know when my children should wash their hands with soap and water.	(RS) I do not know when my pupils should wash their hands with soap and water.
	3	H	(RS) I know that when my children's hands look clean, they are germ free.	(RS) I know that when my pupils hands look clean, they are germ free.
	4	SD	(RS) I know that when surfaces look clean, there are no germs.	(RS) I know that when surfaces look clean, there are no germs.
	5	SD	I know which surfaces I should disinfect in the home.	I know which surfaces I should disinfect in the classroom
Skills An ability or proficiency acquired through practice	6	H	I am able to teach my children to wash their hands.	I am able to teach my pupils to wash their hands.
	7	H	I am able to help my children develop good handwashing habits.	I am able to help my pupils develop good handwashing habits.
	8	H	(RS) I am not able to teach my children to wash their hands.	(RS) I am not able to teach my pupils to wash their hands.
	9	SD	I have the ability to disinfect surfaces in the home.	I have the ability to disinfect surfaces in the classroom
	10	SD	(RS) I do not have the ability to disinfect some of the surfaces in the home.	(RS) I do not have the ability to disinfect some of the surfaces in the classroom
Memory, attention and decision processes The ability to retain information, focus selectively on aspects of the environment and choose between two or more alternatives	11	H	I remind my children to wash their hands before eating.	I remind my pupils to wash their hands before eating.
	12	H	(RS) I forget to remind my children to wash their hands.	(RS) I forget to remind my pupils to wash their hands.
	13	H	(RS) There are many distractions that cause me to forget to remind my children to wash their hands.	(RS) There are many distractions that cause me to forget to remind my pupils to wash their hands.
	14	SD	I remember to disinfect the surface areas in my home every day.	I remember to disinfect the surface areas in the classroom every day.
	15	SD	(RS) I forget to disinfect the surface areas in my home.	(RS) I forget to disinfect the surface areas in the classroom .
Behavioural regulation Anything aimed at managing or changing objectively observed or measured actions	16	H	I check that my children have washed their hands before they eat food to encourage their future hand hygiene.	I check that my pupils have washed their hands before they eat food to encourage their future hand hygiene.
	17	H	(RS) I do not always check if my children wash their hands before eating food.	(RS) I do not always check if my pupils wash their hands before eating food.
	18	H	(RS) I do not always check if my children wash their hand after going to the toilet.	(RS) I do not always check if my pupils wash their hand after going to the toilet.
	19	SD	28. I keep track of whether I have disinfected surfaces in the home.	28. I keep track of whether I have disinfected surfaces in the classroom .
	20	SD	29. (RS) I don't keep track of whether I have disinfected surfaces in my home.	29. (RS) I don't keep track of whether I have disinfected surfaces in the classroom .
Social/professional role and identity A coherent set of behaviours and displayed personal qualities of an individual in a social or work setting	21	H	It is part of my role as a parent to teach my children to wash their hands.	It is part of my role as a teacher to teach my pupils to wash their hands.
	22	H	(RS) It is not my role in society to teach my children to wash their hands.	(RS) It is not my role in society to teach my pupils to wash their hands.
	23	H	(RS) It is not my role in society to tell my children to wash their hands.	(RS) It is not my role in society to tell my pupils to wash their hands.
	24	SD	It is my role as a parent in society is to disinfect surfaces in my home	It is my role as a teacher in society is to disinfect surfaces in my classroom
	25	SD	I feel a social responsibility to disinfect surfaces in my home.	I feel a social responsibility to disinfect surfaces in the classroom
Beliefs about capabilities Acceptance of the truth, reality, or validity about an ability, talent, or facility that a person can put to constructive use	26	H	I believe my children would listen to me if I taught them to wash their hands	I believe my pupils would listen to me if I taught them to wash their hands
	27	H	(RS) I do not believe I can control whether my children wash their hands.	(RS) I do not believe I can control whether my pupils wash their hands.
	28	H	I believe that I can tell my children to wash their hands with soap and water.	I believe that I can tell my pupils to wash their hands with soap and water.
	29	SD	I believe that I am capable of disinfecting surfaces in my home.	I believe that I am capable of disinfecting surfaces in the classroom .
	30	SD	(RS) I believe that there is little I can do to disinfect surfaces in my home.	(RS) I believe that there is little I can do to disinfect surfaces in the classroom
Beliefs about consequences/ Optimism / Reinforcement (Belief) Acceptance of the truth, reality, or validity about outcomes of a behaviour in a given situation (Optimism) The confidence that things will happen for the best or that desired goals will be attained (Reinforcement) Increasing the probability of a response by arranging a dependent relationship, or contingency, between the response and a given stimulus	31	H	I believe that telling my children to wash their hands with soap and water will protect them from falling ill.	I believe that telling my pupils to wash their hands with soap and water will protect them from falling ill.
	32	H	(RS) I believe that children's handwashing habits have little effect on whether they get ill.	(RS) I believe that pupil's handwashing habits have little effect on whether they get ill.
	33	H	(RS) I believe that teaching my children to wash their hands is not worthwhile.	(RS) I believe that teaching my pupils to wash their hands is not worthwhile.
	34	SD	I believe that if I disinfect my home, my children will all fall ill less often.	I believe that if I disinfect the classroom my pupils will all fall ill less often.
	35	SD	(RS) I believe that disinfecting my home has no effect on how often my children get ill.	(RS) I believe that disinfecting my classroom has no effect on how often my pupils get ill.
	36	H	I intend to keep reminding my children to wash their hands before eating.	I intend to keep reminding my pupils to wash their hands before eating.

Intentions / Goals (referred to as: action plans in Dyson et al) (Intentions) A conscious decision to perform a behaviour or a resolve to act in a certain way (Goals) Mental representations of outcomes or end states that an individual wants to achieve	37	H	I intend to keep reminding my children to wash their hands after going to the toilet.	I intend to keep reminding my pupils to wash their hands after going to the toilet.
	38	H	(RS) I do not intend to teach my children to wash their hands.	(RS) I do not intend to teach my pupils to wash their hands.
	39	SD	I intend to regularly disinfect surfaces in my home.	I intend to regularly disinfect surfaces in the classroom .
	40	SD	(RS) I do not intend to regularly disinfect surfaces in my home.	(RS) I do not intend to regularly disinfect surfaces in the classroom .
Emotion A complex reaction pattern, involving experiential, behavioural, and physiological elements, by which the individual attempts to deal with a personally significant matter or event	41	H	(RS) Teaching my children to wash their hands is frustrating.	(RS) Teaching my pupils to wash their hands is frustrating.
	42	H	(RS) Reminding my children to wash their hands is tedious.	(RS) Reminding my pupils to wash their hands is tedious.
	43	H	I enjoy praising my children for washing their hands.	I enjoy praising my pupils for washing their hands.
Environmental context and resources (Any circumstance of a person's situation or environment that discourages or encourages the development of skills and abilities, independence, social competence, and adaptive behaviour)	44	H	(RS) There is not enough time for my children to wash their hands.	(RS) There is not enough time for my pupils to wash their hands.
	45	H	There are practical resources available in my home for my children to wash their hands.	There are practical resources available in my school for my pupils to wash their hands.
	46	H	There are practical resources like running water, available in my home for my children to wash their hands.	There are practical resources like running water, available in my school for my pupils to wash their hands.
	47	SD	(RS) I don't have the time to disinfect surfaces in my home.	(RS) I don't have the time to disinfect surfaces in the classroom .
	48	SD	I have the materials in my home to disinfect surfaces in my home.	I have the materials at my school to disinfect surfaces in the classroom .
Social influences (Those interpersonal processes that can cause individuals to change their thoughts, feelings, or behaviours)	49	H	People around me (such as my partner, family and friends) remind children to wash their hands.	My colleagues remind pupils to wash their hands.
	50	H	Most people in my culture practice good handwashing habits.	Most people in my culture practice good handwashing habits.
	51	H	(RS) It doesn't matter how clean my children's hands are if other people's children are not.	(RS) It doesn't matter how clean my pupil's hands are if other children's are not.
	52	SD	People around me (such as my partner, family and friends) encourage me to disinfect my home.	My colleagues encourage me to disinfect the classroom .
	53	SD	(RS) Few people around me (such as my partner, family and friends) disinfect surfaces in their homes.	(RS) Few of my colleagues disinfect surfaces in the classroom .
Self Confidence Questions		Self confidence	When your [children/pupils] can see you watching them, what percentage of the time do they wash their hands with soap and water after going to the toilet and before eating? [response options 0 - 100%]	When your [children/pupils] can see you watching them, what percentage of the time do they wash their hands with soap and water after going to the toilet and before eating? [response options 0 - 100%]
		Self confidence	When your [children/pupils] cannot see you watching them, what percentage of the time do they wash their hands with soap and water after going to the toilet and before eating? [response options 0 - 100%]	When your [children/pupils] cannot see you watching them, what percentage of the time do they wash their hands with soap and water after going to the toilet and before eating? [response options 0 - 100%]
		Self-confidence	What percentage of the time do you wash your own hands with soap and water after going to the toilet and before eating? [response options 0-100%]	

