Appendix A presents a list of the domains, their definitions, and survey items about hand-hygiene influencing.

The hand hygiene items will appear in a random order.

In the final survey, we aim to assess each of 11 behavioral determinates using at least 3 items that can be responded to with a 5-point Likert scales, where 1=strongly disagree and 5=strongly agree. Some items will be reverse scored to mitigate acquiescence bias.

- **Survey Section 4: Surface disinfecting.**

Appendix A presents a list of the domains, their definitions and survey items about hand-hygiene influencing.

The surface cleaning items will appear in a random order.

In the final survey, we aim to assess each of 11 behavioral determinates using at least 1 item that can be responded to with a 5-point Likert scales, where 1=strongly disagree and 5=strongly agree. Some items will be reverse scored to mitigate acquiescence bias.

- **Survey Section 5: Self-reported confidence (3 items).**

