## 12b. Statistical methods

As a reminder, the sample-size is designed to support a factor analysis for the hand-hygiene component of the project. The surface cleaning component of the project will only be analyzed using descriptive and exploratory methods.

Software: The data will be analysed using the most recently available copies of SPSS and SPSS: AMOS.

Descriptive: Frequencies, percentages, averages and confidence intervals will be used to describe the participants' responses and demographics.

Internal Consistency: Cronbach's alphas will be calculated. Items will be removed as necessary to achieve an alpha coefficient of 0.70 or above within each domain; those coefficients as low as 0.65 will be tolerated if necessary to retain the planned model.

[figure not shown]
Confirmatory Factor Analyses (CFA) - Objective 4: CFA will be performed to test whether the data from the items fit within the pre-determined components.

The first models (the primary analyses) will be conducted with the data from all the countries and then additional models (the secondary analyses) will be conducted with each country.

The models will be specified in AMOS and tested for goodness of fit using three indices: (a) absolute fit (based on a Chi-squared to degrees of freedom ratio, less than 2; ), (b) parsimony (based on Root Mean Square Error of Approximation (RMSEA) of close to or less than 0.06), and comparative fit (based on an index 'close to' 0.95; ). The models may be revised until the desired measures of fit are obtained.

Figure will be created to describe the final models' structure. An example of a figure like this with only 2 determinates appears below (Figure 2):

Figure 2. Example of a CFA model

Regression analyses - Objective 5: Multiple regression analysis will be conducted, overall and for each country. The predictors will be participants' average responses to each behavioural determinate, and the outcome will be participants' average responses to the confidence items. An alpha value of 0.05 will be used to assess each predictors' contribution to the overall model.

Exploratory Analyses - Objective 6: The participants' individual differences will be compared using graphical analyses (bar charts with error bars) and statistical tests (e.g., ANOVAs). Their content is not further specified within this protocol.

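### Knowledge items 3 and 4 put a claim to know before a statement keyed as false and are reverse scored, so disagreeing out of ignorance scores on the knowledgeable side

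*Combined protocol and SAP*

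**What the plan says.** Appendix A defines the Knowledge domain as "An awareness of the existence of something" and gives it three hand-hygiene items and two surface items. The parent wordings are below; the teacher versions have the same structure and the same RS flags.

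- Item 1 (hand hygiene, not reversed): "I know that my children should wash their hands with soap and water for at least 20 seconds".
- Item 2 (hand hygiene, reversed): "RS) I do not know when my children should wash their hands with soap and water".
- Item 3 (hand hygiene, reversed): "RS) I know that when my children's hands look clean, they are germ free".
- Item 4 (surface, reversed): "RS) I know that when surfaces look clean, there are no germs".

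Section 11 specifies "5-point Likert scales, where 1=strongly disagree and 5=strongly agree" and gives one reason for reversal: "Some items will be reverse scored to mitigate acquiescence bias". It describes no option for not knowing. Under Section 11b, a respondent who does not wish to answer an item withdraws, and incomplete surveys are not analysed.

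Section 12b sets the reliability rule: "Items will be removed as necessary to achieve an alpha coefficient of 0.70 or above within each domain", with values down to 0.65 tolerated if needed to keep the planned model. The same section uses domain averages as regression predictors and confines surface items to descriptive and exploratory work. Sections 11 and 12a call for at least three hand-hygiene items per domain.

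**The concern.** Items 3 and 4 each contain two claims: that the respondent knows something, and that the thing is so. The RS flag shows that the plan treats the second claim as false. A respondent who knows that clean-looking hands can carry germs will disagree. A respondent with no view either way can also disagree, because the claim to know is untrue for them. Reversal puts both on the knowledgeable side, although the second lacks the awareness by which the domain is defined.

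Item 1 has the same stem without this problem: its statement is keyed as correct, so a respondent who disagrees scores low whatever the reason. Item 2 scores admitted ignorance low. One three-item domain can therefore score the same lack of knowledge in opposite directions.

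At stake is whether the survey detects lack of knowledge, one of the barriers it is meant to identify. Opposite scoring could also weaken item 3's correlation with items 1 and 2, and so the domain alpha.

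**Working it through.** The plan states no figure on this point, so there is none to reproduce.

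**Scoring.** On a 1 to 5 scale the reversed score is 6 − raw (implied by the scale, not written in the plan): 1→5, 2→4, 3→3, 4→2, 5→1. Items 2 and 3 are reversed and item 1 is not. The answer patterns are constructed for illustration.

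| Respondent | Raw, items 1, 2, 3 | Scored | Mean |
|---|---|---|---|
| Fully informed | 5, 1, 1 | 5, 5, 5 | 5.00 |
| Unsure, mild answers, item 3 taken literally | 2, 4, 2 | 2, 2, 4 | 8/3 = 2.67 |
| Same person, midpoint on item 3 | 2, 4, 3 | 2, 2, 3 | 7/3 = 2.33 |
| Unsure, extreme answers, item 3 taken literally | 1, 5, 1 | 1, 1, 5 | 7/3 = 2.33 |
| Same person, midpoint on item 3 | 1, 5, 3 | 1, 1, 3 | 5/3 = 1.67 |

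The wording therefore raises the average by 2.67 − 2.33, about 0.33, for mild answers, and by 2.33 − 1.67, about 0.67, for extreme ones. This applies only to a respondent who takes the stem literally.

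**Alpha from assumed correlations.** For three standardised items, alpha = 3r̄/(1 + 2r̄), with r̄ = (r₁₂ + 2r)/3. Here r₁₂ is the correlation between items 1 and 2, and r is that of item 3 with each of them. The documents give neither; r₁₂ = 0.5 is assumed.

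| r | r̄ | alpha |
|---|---|---|
| 0 | 0.167 | 0.38 |
| 0.1 | 0.233 | 0.48 |
| 0.2 | 0.300 | 0.56 |
| 0.3 | 0.367 | 0.63 |
| 0.35 | 0.400 | 0.67 |
| 0.4 | 0.433 | 0.70 (0.696) |
| 0.5 | 0.500 | 0.75 |

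Setting alpha = 0.65 gives r̄ = 0.65/1.7 = 0.382, so r = (3 × 0.382 − 0.5)/2 ≈ 0.32. Below that the domain misses the tolerated limit; above it the domain meets it. With r₁₂ = 0.6 and r = 0.3, r̄ = 0.4 and alpha is 0.67.

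**Alpha from an assumed share of literal readers.** This was simulated with 200,000 respondents, three five-category items and an assumed loading of 0.7 each. A chosen share of the half with below-average knowledge answered item 3 as if equally far above average.

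| Share of lower half reading literally | alpha |
|---|---|
| 0% | 0.71 |
| 10% | 0.68 |
| 20% | 0.66 |
| 30% | 0.63 |
| 50% | 0.57 |

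Under these assumptions alpha is still above 0.65 at 20% and below it at 30%.

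**Removing item 3.** Knowledge would have 3 − 1 = 2 hand-hygiene items, against a planned minimum of three.

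**The case against.** The strongest reply is that the harm depends on behaviour the documents do not describe. A respondent may ignore the stem and answer the embedded statement, in which case the reversal is right. An unsure respondent can already choose the middle of the scale. The items drew on the literature, expert advice and a pilot, and the alpha and model-revision steps would screen a poor item. This stands as a limit on size. It does not remove the ambiguity: no pilot results are given for this item, back-translation would carry an ambiguity in the English into the other languages, and screening out item 3 leaves the domain below its planned minimum.

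The constructed respondent is also uninformed on everything. Item 3 covers a different fact from items 1 and 2, so a person may know some and not others, and a low correlation could persist after rewording. That stands too.

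Three stronger readings are tempting but unsupported.

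- **That the uninformed respondent is scored as most knowledgeable.** The top score needs strong disagreement; plain disagreement scores 4.
- **That the average should have been 2.0 rather than 2.67.** That requires a score of 2 on item 3, meaning agreement with the false statement. This is a misconception, not uncertainty; the fair comparison is 2.33.
- **That the wording makes alpha fall below 0.65.** This holds only for some of the assumed values above.

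**Conclusion.** The ambiguity and the opposite scoring within the domain follow directly from Appendix A and the response scale. They rest on two inferences: that RS means reverse scored, and that the key therefore treats the embedded statements as false.

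The size is uncertain. For one literal reader with mild answers the Knowledge average rises by about 0.33 points. The effect on the overall mean and on alpha cannot be estimated from the documents, and an upward bias among the uninformed is conditional, not established.

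Item 3 is one of 33 hand-hygiene items (11 domains × 3) but a third of its domain, and it feeds the primary analysis. Item 4 is one of two surface Knowledge items and carries less weight. This is a modest fault, worth correcting because correction is cheap.

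**What to change.** Delete the opening words 'I know that' from items 3 and 4 in both the parent and teacher columns, so that each begins at 'When', and keep the RS flag. Agreement then shows the misconception, disagreement rejects it, and an unsure respondent has a natural midpoint. Removing the RS flag instead would be wrong, because it would reward the misconception.

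The cost is four wording edits (two items × two versions), with no change to survey length or analysis. There are three downsides:

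- The two items would differ from any version used in the pilot.
- Appendix A is headed as finalized. Section 11 still describes translation as a future step, but any translation and back-translation of these items already done would have to be repeated.
- Item 3 would become a factual-belief item beside two self-reported-knowledge items, so its correlation with them may stay modest. The report should say so when it presents the Knowledge alpha.

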To inform the development of future school-based interventions, the current study seeks to develop a survey to identify the most common reasons adults are not already positively influencing school children’s hand-hygiene. Identifying the most common reasons is important, because interventions that target uncommon or misinformed reasons are unlikely to yield practically significant improvements. The list of possible reasons includes the behavioral determinates described by the Theoretical Domains Framework (TDF;). Specifically, the present study aims to assess adults’ tendencies to positively influence children’s hand-hygiene with regards to their: Knowledge, Skills, Memory, attention and decision processes, Behavioral regulation, Social/professional role and identity, Beliefs about capabilities, Beliefs about consequences (inclusive of Optimism and Reinforcement), Intentions (inclusive of Goals), Emotion, Environmental context and resources, and Social influences.

In the current study, a survey will be designed to measure each TDF domain. In addition, because the cleanliness of the surrounding environment also influence cleaning behaviors, a sub-component of the survey will assess adults’ tendencies to disinfect surface areas where children play and learn. The survey will be rolled-out across several countries/regions. The primary and secondary analyses will to validate the internal and external features of the hand-hygiene survey component. Secondary analyses will look at the surveys external validity and internal validity across each country/region. Exploratory analysis will be used to compare participants’ responses across countries/regions, and individual differences. The results of this survey will be used to inform a future school-based intervention.

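### Two of the three hand-hygiene Intentions items presuppose that the adult already reminds, so adults who intend to start are likely to score too low or ambiguously

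*Combined protocol and SAP*

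**What the plan says.** Section 2 (Introduction/Background) sets the purpose of the survey: to identify "the most common reasons adults are not already positively influencing school" children's hand hygiene. Adults who do not yet do so are therefore the group of interest.

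Appendix A defines intention as "A conscious decision to perform a behaviour or a resolve to act in a certain way". Nothing in that definition requires the behaviour to be under way. The domain has three hand-hygiene items, given here in the parent version:

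- Item 36: "I intend to keep reminding my children to wash their hands before eating".
- Item 37: "I intend to keep reminding my children to wash their hands after going to the toilet".
- Item 38, reverse scored: "RS) I do not intend to teach my children to wash their hands".

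The teacher versions of items 36 and 37 differ only in referring to pupils. The surface-disinfecting items of the same domain (39 and 40) do not presuppose current behaviour; item 39 reads "I intend to regularly disinfect surfaces in my home".

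Three other provisions bear on the point. Section 11 (Survey Section 3) specifies a five-point agreement scale and describes no option for *not applicable*. Under Section 11b, a participant who does not want to answer an item can only leave the survey, and incomplete surveys are not analysed. Section 12b uses the average response per determinant as the regression predictor, and allows items to be removed until Cronbach's alpha reaches 0.70, with 0.65 tolerated if needed.

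**The concern.** The word *keep* in items 36 and 37 makes each item a statement about two things: that the adult reminds now, and that the adult means to go on. Someone who does not remind but has decided to start agrees with the intention and not with the premise. Disagreeing gives a low intention score, agreeing endorses a premise that is untrue, and a neutral answer cannot be interpreted. The scale and the completion rule leave no other choice short of withdrawing.

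Current behaviour is therefore mixed into two thirds of the Intentions score, and the ambiguity falls on the people the survey is meant to explain. In the descriptive comparisons (Objective 4), Intentions could look like a larger barrier than it is. In the regression on the confidence items (Objective 3), its coefficient would be harder to read as an effect of intention, because the score partly reflects whether the adult already reminds. Section 2 itself warns that interventions aimed at uncommon or misinformed reasons are unlikely to help much.

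**Working it through.** The plan states no figure that depends on this wording, so there is none to reproduce. The check is a comparison of wording followed by an illustration.

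**1. Which items are affected.** In the extracted table, row 36 stands just before the Intentions label because of a page break. The numbering (31-35 for the preceding domain, 36-40 for this one, each with three hand-hygiene and two surface items) and the wording both place item 36 in Intentions. The hand-hygiene items are 36, 37 and 38, and two of the three contain *keep*.

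**2. Domain mean.** With item 38 reversed on the 1-5 scale,

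mean = (item 36 + item 37 + (6 − item 38)) / 3.

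Items 36 and 37 carry 2/3 of the weight.

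**3. One respondent.** Take an adult who does not remind, intends to, and answers 2 on item 38 (reversed to 4). Assume that without *keep* this person would answer 4 on items 36 and 37, giving (4 + 4 + 4)/3 = 4.00. Under the present wording:

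| Answer to items 36 and 37 | Mean | Shortfall from 4.00 |
|---|---|---|
| 2 | (2 + 2 + 4)/3 = 2.67 | 1.33 |
| 3 | (3 + 3 + 4)/3 = 3.33 | 0.67 |
| 4 | (4 + 4 + 4)/3 = 4.00 | 0 |

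For a person with the strongest intention (item 38 answered 1, reversed to 5), the mean runs from (1 + 1 + 5)/3 = 2.33 to (5 + 5 + 5)/3 = 5.00, depending only on how *keep* is read. An equally committed adult who already reminds scores 5.00. A non-reminder with no intention scores (1 + 1 + 1)/3 = 1.00.

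**4. If item 38 is removed under the alpha rule.** The score is then the average of items 36 and 37 alone. Answers of 1, 2 or 3 give 1.00, 2.00 or 3.00, and at 1 a committed non-reminder cannot be told apart from someone with no intention.

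**5. Shift in the overall mean.** Let q be the share of adults who do not yet remind and h the share of those who intend to. Neither is in the documents; assume q = 0.10 to 0.30 and h = 0.5, so q × h = 0.05 to 0.15. With item 38 kept, the shift is shortfall × q × h:

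- Answers of 2: 1.33 × 0.05 = 0.07, to 1.33 × 0.15 = 0.20.
- Answers of 3: 0.67 × 0.05 = 0.03, to 0.67 × 0.15 = 0.10.
- Answers of 4: 0.

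Over answers of 2 to 4 the range is 0 to 0.20 points.

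**The case against.** The strongest reply is that the wording is merely ambiguous. *Keep reminding* can be read as *remind repeatedly*, which an adult who means to start can endorse, and then there is no bias. The documents give no data on how such respondents answer or how many there are. The item list was informed by a pilot whose results are not in the documents and which might support the wording. Nor is item 39 an exact model: it includes an adverb of regularity, and removing *keep* loses some sense of persistence. All of this stands as a limit on size and certainty. It does not remove the presupposition, and a score that depends on how one word is read is itself a measurement problem.

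A reader might infer more than the documents support, in three ways:

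- *That non-reminders cannot express an intention and are scored as lacking it.* Item 38 lets them reject the statement that they do not intend to teach handwashing. While it is kept, the respondent with the strongest intention scores at least 2.33, not 1.00.
- *That 5-15% of the sample (q × h) would be counted as lacking intention.* Section 12b uses averages. It sets no cut-off and counts nobody as lacking a domain.
- *That item 11 in the Memory domain has the same fault and needs the same repair.* It reads "I remind my children to wash their hands before eating", which does report behaviour. But items 12 and 13 ask directly about forgetting: with 2 on item 11 and 4 on each of the other two after reversal, the Memory mean is (2 + 4 + 4)/3 = 3.33, above neutral. Rewording it after its surface counterpart, "I remember to disinfect the surface areas in my home every day", would not help, since someone who does not remind for reasons of role or belief could not readily agree with that form either.

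**Conclusion.** The point holds for items 36 and 37, in the parent and teacher versions. Their wording presupposes the behaviour whose absence the survey sets out to explain, it goes beyond the plan's own definition of intention, and the surface items of the same domain manage without it. Non-reminders who intend to start are likely to score too low or ambiguously on two thirds of the Intentions average. Item 38 is only a partial safeguard, because it concerns teaching rather than reminding and may be removed.

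The size is unknown. The 0 to 0.20 point shift in the overall mean rests on the assumed 10-30% and one half, on answers between 2 and 4, and on item 38 being kept. The effect on the overall mean may be small; the shortfall for an affected individual, up to 1.33 points in the same illustration, is not. The direction and the remedy are clear enough to justify changing the wording before launch.

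**What to change.** Before launch, change the opening of items 36 and 37 to *I intend to remind*, in the parent and teacher versions, following the pattern of items 39 and 40. Leave the rest of each item as it is. Put both items through the translation and back-translation steps already planned in Table 1.

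The cost is re-translation of two items and a departure from the pilot-informed list marked as finalized 09-Apr-2020, which should be noted in the protocol. Sample size and analysis methods do not change.

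If the present wording has already been fielded, state the limitation in the report and show item 38 separately alongside the Intentions average.
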